### Exploratory objectives:

- a) To describe the immune contexture in residual tumors of patients with high risk TNBC after receiving neoadjuvant chemotherapy
- b) Tissue banking for future studies (NGS of initial biopsy and surgical specimen), plasma, PBMCs

## **8.2 Sample Size Considerations**

The primary objective of the study is to assess the change in PIS, the Peripheral ImmunoScore, at 6 weeks (=2 cycles) from baseline, in each arm.

The sample size of 15 per arm (45 totally for 3 arms) is mainly based on the feasibility of patient accrual. A sample size of 15 per arm will have about 85% power to detect an effect size of 1 (the difference of the change in PIS from baseline to week 6 between two arms divided by the standard deviation) at 5% significance level.

## **8.3. Randomization and Stratification Factors**

Stratified randomization will be used to assign patients into the three arms. There will be three strata: nivolumab (arm A), capecitabine (arm B) and nivolumab/capecitabine combo (arm C). Within each stratum, blocked randomization with randomly selected block sizes will

be used. The stratified randomization procedure will be carried out by the biostatistician(s) at the LCCC Biostatistics and Bioinformatics Shared Resource. They will implement the randomization, such as generate the randomization table and hold the randomization key.

## **8.4 Endpoints**

### **8.4.1. Primary Endpoint**

a. Quantification of immune activation measured by changes of PIS from baseline to week 6 in each arm.

### **8.4.2 Secondary Endpoints**

- a. Quantification of immune activation measured by changes of PIS from baseline to week 12 in each arm.
- b. Quantification of grade 3 and 4 toxicities according to the National Cancer Institute Common Toxicity Criteria for Adverse Events Version 4.0 [NCI CTCAE v4.03]
- c. Association between changes in PIS from baseline to week 6 and week 12 and clinical outcome variables (DRFS and OS at 2-years). Distant recurrence free survival (DRFS) is defined by time from study enrollment to date of first invasive distant disease recurrence, second invasive primary cancer (breast or not), or death due to any cause.
- d. To describe the following endpoints and compare them between arms: DRFS, OS
- e. Quantification of ct-DNA at different time points

### **8.4.3 Exploratory Endpoints**

- f. Quantification of immune activation by IHC, flow cytometry and ELISA analysis
- g. Quantification of antigen-specific responses by intracellular cytokine staining and CD8+ T-cell clonal expansion

## **8.5 Analysis Plan**

### **8.5.1. Analysis for the Primary Endpoint**

For the primary endpoint, the observed change of PIS from baseline to week 6 in each arm will be presented with its 95% confidence interval. The difference of the change of PIS between treatment arms will be compared using two-sample t-test.

For a patient to be evaluable for immunomodulation, measured by the peripheral immunoscore, by nivolumab, capecitabine or the combo, the patient must complete the first 2 cycles. Any patient who is taken off study prior to completion of 2 cycles must be replaced.

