Diagnosis and Main Inclusion and Exclusion Criteria	
Key Inclusion Criteria: Biopsy proven TNBC (ER and PR defined as <math>\leq 5\%</math> cells stain positive), HER2 negativity defined as (IHC0, 1+ without in situ hybridization (ISH) HER2/neu chromosome 17 ratio OR IHC 2+ and ISH HER2/neu chromosome 17 ratio non-amplified with ratio <math>< 2.0</math> and if reported average HER2 copy number <math>< 6</math> signals/cells); residual disease of <math>\geq 1.0</math> cm of the primary tumor and/or node positive disease measuring <math>\geq 0.5</math>cm; receipt of neoadjuvant taxane +/- anthracycline; platinum use allowed; must have completed definitive resection of primary tumor; signed ICF; age <math>\geq 18</math>.
 
Key Exclusion Criteria: Stage IV disease; previous exposure to capecitabine, fluorouracil or immunotherapy with anti-PD1, anti PDL1 or anti-CTLA4; active autoimmune disease requiring systemic treatment in the past 2 years; tuberculosis, hepatitis B or C, HIV or other active infection; chronic use of systemic steroids or pregnancy.

Study Design	
Pilot phase II open-label three arm randomized trial of nivolumab, capecitabine or combination as adjuvant therapy for 45 patients with residual TNBC after adequate neoadjuvant chemotherapy followed by definitive surgery. Patients are randomly assigned to 1 of 3 treatment arms: ARM A – Nivolumab 360 mg iv q3weeks for x 6 cycles; ARM B - Capecitabine 1250mg/m^2 bid D1-D14 q3 weeks x 6 cycles; ARM C - Nivolumab 360mg iv q3weeks + Capecitabine 1250mg/m^2 bid D1-D14 q3 weeks x 6 cycles. We will enroll 15 patients per arm (45 totally for 3 arms).

Duration of therapy	
All drugs will be administered for 18 weeks, or until disease progression or unacceptable toxicity is observed.

Sample size considerations	
The primary objective of the study is to assess the change in PIS, the Peripheral ImmunoScore, at 6 weeks (=2 cycles) from baseline, in each arm. The sample size of 15 per arm (45 totally for 3 arms) is mainly based on the feasibility of patient accrual. A sample size of 15 per arm will have about 85% power to detect an effect size of 1 (the difference of the change in PIS from baseline to week 6 between two arms divided by the standard deviation) at 5% significance level.

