## 6.0 STUDY PROCEDURES AND TREATMENT ASSIGNMENT

### 6.1. Table of events

	Pre-registration	Screening	On Study (maximum 6 cycles; cycle is every 21 d)	Treatment discontinuation	Surveillance
	Post-surgery	-30 days	D1 of each cycle +/- 7 days. Each cycle is 21 days.	30 days (+/-7 days) after last dose	
Assessments					
Informed consent	X				
Medical history and height		X			
Physical examination		X	X ^	X	
Weight, BP		X	X ^	X	
ECOG PS		X	X ^	X	
CMP		X	X	X	
Creatinine clearance		X	X	X	
CBC with differential		X	X	X	
Breast imaging (remaining tissue only)					Yearly +/- 30 days
Adverse event and con meds assessment		X	X ^		
Urine pregnancy or serum HCG for WOCBP only		X	X ^ (every 3 weeks) for Arm A and C		
ACTH and Thyroid Function Tests#		X	X ^ (week 12) for Arm A and C	X	
Hepatitis and HIV screening*		X			
EORTC QLQ-C30 &		X	X (week 6)	X	
Telephone communication or focused physical exam+					Every 3-6 months
Treatment					
			Nivolumab 360mg iv q3w; capecitabine 1250mg/m  D1-14		

Correlative Samples					
Tumor from initial diagnosis		X (if available)			
Tumor from definitive surgery – with IHC testing for MSI	X				
Serum for peripheral immunoscore			X ^ (baseline, week 6 and 12)	X (if recurrence)	
Blood for ct-DNA \$			X ^ \$ (baseline, week 6 and 12)	X (if recurrence)	
Tumor from metastatic site				X (if recurrence)	

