## **8.0. STATISTICAL CONSIDERATIONS**

### **8.1 Objectives**

### Primary objective:

- 2) To assess the immunologic effects of capecitabine, nivolumab or the combo, post neoadjuvant and post-surgery, in the adjuvant setting, in patients with high risk TNBC as defined by presence of residual disease (breast and or LNs) at surgery, in terms of the change of PIS.
  - a) We hypothesized that among patients with TNBC and residual disease at the time of surgery, the change of the Peripheral ImmunoScore (PIS) from baseline to week 6 will be higher among those who receive post-surgery immunotherapy (ARM A and C), compared to those who receive post-surgery chemotherapy alone (ARM B).

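### The primary PIS comparison (8.5.1) omits baseline PIS as a covariate, and the 85% power in 8.2 is reproduced only by a one-sided test that the plan never states

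*Combined protocol and SAP*

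**What the plan says.** Section 8.5.1 reports the week-6 change in PIS per arm with a 95% confidence interval and then makes the between-arm comparison: "The difference of the change of PIS between treatment arms will be compared using two-sample t-test". It names no covariate, arms or sidedness.

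Section 8.1 (and 2.1) gives the hypothesis for the week-6 change in PIS, namely that it "will be higher among those who receive post-surgery immunotherapy (ARM A and C), compared to those who receive post-surgery chemotherapy alone (ARM B". Section 8.4.1 words the endpoint within arms: "Quantification of immune activation measured by changes of PIS from baseline to week 6 in each arm". Section 8.4.2 has the week-12 counterpart: "Quantification of immune activation measured by changes of PIS from baseline to week 12 in each arm".

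On size, Section 8.2 states "The sample size of 15 per arm (45 totally for 3 arms) is mainly based on the feasibility of patient accrual", followed by "A sample size of 15 per arm will have about 85% power to detect an effect size of 1". The effect size is defined there and in the synopsis as "the difference of the change in PIS from baseline to week 6 between two arms divided by the standard deviation) at 5% significance level".

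In the table of events (6.1), the row "Serum for peripheral immunoscore" schedules samples at baseline, week 6 and week 12.

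**The concern.** Three gaps bear on how the primary result will be produced and read.

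- **Covariate.** A change score uses baseline PIS only by subtracting it. A model that also contains baseline as a covariate usually estimates the arm difference more precisely, from samples already planned. With 15 patients per arm, precision is scarce.
- **Sidedness.** A reader who takes the 5% level as two-sided, as is common, will credit the trial with about 10 points more power than it has for one pair of arms.
- **Pooled or separate.** With three arms, a two-sample test needs two groups. Section 8.1 can be read as A and C together against B. Section 8.2 speaks of two arms and Section 8.4.1 of each arm, which points to A against B and C against B separately. The two readings have different power and different error rates.

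**Working it through.** **Inputs.** From Section 8.2: n = 15 per arm, effect size d = 1 (difference in change divided by its SD), level 5%. From Section 8.5.1: two-sample t-test, with replacement of patients who leave before completing two cycles, so 15 evaluable per arm is assumed.

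**1. Reproducing the stated power.** For two arms of 15, df = 15 + 15 − 2 = 28 and the noncentrality is d / √(2/n) = 1 / √(2/15) = 2.739.

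| Test, one pair | Critical t (28 df) | Power |
|---|---|---|
| One-sided 5% | 1.701 | 84.8% |
| Two-sided 5% | 2.048 | 75.3% |

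Only the one-sided figure matches about 85%; the gap is 84.8 − 75.3 = 9.5 points. Two-sided power of 85% would need an effect size of 1.13 at 15 per arm, or 19 per arm (85.1%; 18 per arm gives 83.0%).

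**2. Pooled reading.** For A and C together (30) against B (15), the noncentrality is 1 / √(1/30 + 1/15) = 3.162 on 43 df. Power is 87.1% two-sided and 92.9% one-sided if both nivolumab arms have effect size 1. Neither is the comparison that Section 8.2 describes.

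**3. Baseline as covariate.** Let r be the correlation of baseline with week-6 PIS and k the ratio of week-6 SD to baseline SD. Relative to the change-score variance, the residual variance after adjustment is

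f = k²(1 − r²) / (1 + k² − 2rk).

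With k = 1 this reduces to (1 + r)/2. The noncentrality becomes 2.739 / √f, with one degree of freedom less (27 for a pair). The documents give neither r nor k, so the values below are assumptions.

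| r (k = 1) | f | Two-sided power, one pair |
|---|---|---|
| no covariate | 1 | 75.3% |
| 0.3 | 0.65 | 90.6% |
| 0.5 | 0.75 | 86.2% |
| 0.7 | 0.85 | 81.7% |
| 0.9 | 0.95 | 77.3% |

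A simulation of the full three-arm model (41 df, 40,000 trials per cell) gave 90.6%, 86.1%, 81.9% and 77.0%. In the two null cells checked it rejected in 5.0% to 5.2%.

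Over a wider grid (k from 0.75 to 2, same r), simulated power ran from 75% (no gain) to 97% (k = 0.75, r = 0.3). The gain vanishes when r × k = 1. For example, r = 0.5 and k = 2 gives f = 4 × 0.75 / (1 + 4 − 2) = 1, with simulated power 75.0% against 75.3% for the planned test.

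**4. Error rate if A−B and C−B are both tested unadjusted.** When no arm differs, simulation (400,000 trials) puts the chance of falsely finding A or C higher than B at 4.5% with two-sided 5% tests and 8.7% with one-sided 5% tests.

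**The case against.** Much of the case on the other side stands.

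- A reader might infer that 85% is a **power miscalculation**. The documents do not support that. The hypothesis is directional, and a one-sided 5% test gives 84.8%. What is missing is the statement of sidedness. The per-arm 95% intervals do not settle it, because they concern within-arm change.
- A reader might infer that the plan leaves the **deciding comparison wholly open** to choice after the data are seen. It does not. Sections 2.1 and 8.1 fix the arms (A and C against B), the time (week 6) and the direction, and 8.5.1 fixes the test. Comparing A with C is not part of the hypothesis. Only pooled versus separate, and sidedness, remain.
- A reader might infer that the **t-test is biased or invalid** without the covariate. Under randomisation it is neither.
- A reader might infer a **general inflation of false positives**. With two-sided tests the directional rate is 4.5%; it exceeds 5% only under separate, unadjusted one-sided tests.
- The size of the covariate's gain is unknown, and the documents give no numeric scoring rule for PIS from which to judge linearity. This limits how much can be promised. The cost remains one degree of freedom, so the worst case in the grid is practically no loss.
- The trial is a pilot sized mainly on feasibility. That explains 15 per arm, but it is no reason to leave the sidedness unstated or collected baseline data unused.

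**Conclusion.** The point holds as an improvement and a clarification, not as an error in the plan. The planned test is valid but leaves possible precision unused. Under equal SDs, two-sided power for one pair would rise from 75% to between 77% and 91% for assumed correlations of 0.9 down to 0.3; for other SD ratios the gain ranges from none to large. The stated 85% is right for a one-sided test of two arms of 15 and about 10 points too high if the test is two-sided, and no section says which applies. Pooled versus separate comparison of A and C with B is also unstated. These conclusions assume 15 evaluable patients per arm, roughly normal change scores with a common SD and, for the covariate, a roughly linear relation with baseline. They affect how precisely the primary result is estimated and how it is read, not its validity.

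**What to change.** 1. In 8.5.1, replace the t-test sentence with: *Week-6 PIS change from baseline will be analysed by a linear model with arm (A, B, C) and baseline PIS; arm differences are given with 95% confidence intervals.* This keeps change as the endpoint and gives the same arm differences as modelling week-6 PIS, since subtracting baseline from the outcome alters only the baseline coefficient. Keep the per-arm change with its 95% interval, and use the same model at week 12.
2. In 8.2 and the synopsis, give the power with its sidedness: for one pair before adjustment, 85% one-sided or 75% two-sided.
3. In 8.5.1, say whether A and C are pooled against B or each compared with B, and match the power sentence to that choice. The choice is the sponsor's and is a trade-off. These figures are without baseline adjustment:
   - The contrast (A+C)/2 − B (42 df) has 87% power two-sided or 93% one-sided if both nivolumab arms have effect size 1, but 34% or 46% if only one does.
   - Separate pair tests (28 df) under a rule such as Holm have 65% or 75% for the working arm if only one works, and 80% or 88% for at least one if both do.

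**Cost.** No new patients, samples or visits. The model uses one degree of freedom and assumes rough linearity in baseline PIS. The edits are to protocol text, and Section 10.1 requires IRB approval of amendments.

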### **8.5.2. Analysis for the Secondary Endpoint**

The observed incidence of toxicity will be tabulated according to the grade level and the attribution using the National Cancer Institute CTCAE v. 4.0. Fisher's Exact test will be used to compare the incidence rate of toxicity between treatment groups. We expect that among

patients with TNBC and residual disease at the time of surgery, those who receive post-surgery immunotherapy (ARM A and C) will have longer invasive disease-free survival (DRFS) time compared to those who receive post-surgery chemotherapy alone (ARM B). Patients will be followed for DRFS and overall survival (OS) for 3 years. The Kaplan-Meier method will be used to analyze the DRFS and OS. The DRFS and OS at year 2 will be presented with their 95% confidence intervals. Log-rank test will be used to compare the DRFS and OS between treatment groups.

## **9.0 CORRELATIVE RESEARCH**

### **9.1 Peripheral Immunoscore**

We selected the refined PIS as a surrogate of clinical benefit and a new strategy to identify patients with TNBC and high-risk disease who may benefit from immunotherapy to eliminate residual micrometastasis. The peripheral immunoscore was calculated based on a predefined analyses of refined immune cell subsets for which a biologic function had been previously reported revealed statistically significant improved PFS ( $P < 0.001$ ) in patients with metastatic breast cancer receiving docetaxel plus immunotherapy compared to docetaxel alone (Fig 2). To calculate the PIS, flow cytometry was performed on PBMC harvested at different time points. A multiparametric flow cytometry platform was applied to measure the frequency of PBMC. Patients' PBMCs by density gradient separation, and then 1 mL of PBMCs was cryopreserved in liquid nitrogen at a concentration of 107 cells/mL per vial. On the day of staining, one vial of cryopreserved PBMCs per patient was defrosted, cells were counted, and then stained with the appropriate monoclonal antibodies. Table 1 shows the classic immune cell types as well as those refined subsets with a phenotype reflecting immune function. Viability of all samples following thawing after cryopreservation was 80% to 95%. The frequency of individual subsets was calculated as a percentage of total PBMCs to help reduce the bias that could occur in the smaller subpopulations with fluctuations in parental leukocyte populations. The PIS defined by Farsaci et al was selected based on being the closest to the particular scenario proposed on the OXEL study. This has been validated in a group of patients with metastatic BC receiving docetaxel and immunotherapy, and shown to be predictive of PFS. While this (and other) immune biomarkers in the blood available today have not been validated in all clinical scenarios – including early BC – available data suggests that this immunoscore constitutes a promising surrogate marker of clinical outcome in this group of patients. The PIS will be performed 40) at [name] lab at NIH, which developed this particular immunoscore.

### **9.2 Immune contexture in residual tumors**

We will evaluate PD-L1 expression in the tumor, expression of other immune checkpoints that may be upregulated (e.g., LAG3, TIM3, ICOS) and expression of the cellular composition (CD8+, activated T cells, CD4+, T regs, MDSC and macrophages) using the Perkin Elmer Vectra 3.0 Automated Quantitative Pathology Imaging System, which is housed in the Lombardi Histopathology and Tissue Shared Resource (HTSR). We will also measure other

cytokines and chemokines involved in the immune system activation by Nanostring, as described in Table 2. Based on preclinical studies of immune regulation of tumor growth we will specifically examine CD47, TGFβ1, Sgpl1, Tex9 and Pex14 in the tumor specimens by PCR and IHC. All tissues will be processed in [name] laboratory and assays will be performed in the Lombardi HTSR (IHC) and the Lombardi Genomics and Epigenomics Shared Resource (Nanostring, PCR).

	Prioritized for Analysis
Immunologic profile (Vectra 3.0 IHC)	PDL1, LAG3, TIM3, ICOS, other checkpoints
Cellular and molecular composition of residual tumor (Vectra 3.0)	CD8+, CD4+, Tregs, MDSC, PD1, other checkpoints
Other cytokines and chemokines (Nanostring)	IL-2, 4, 6, 8, 10, 17; IFN- $\beta$ , $\gamma$ ; TNF- $\alpha$ ; STING;
Other candidate resistance biomarkers (qPCR, Vectra 3.0 IHC)	CD47, TGFβ1, Sgpl1, Tex9 and Pex14

Table 2. Immune Biomarkers to be Studied

### **9.3. Sample Labeling Overview**

Patients will be de-identified and labeled with the following study label (XXX-XXXX-XX-OXEL):

- The first three letters will be the site name.
  - GUH = Georgetown
  - WHC = Washington Hospital Center
  - HCK = Hackensack
  - UOC = Univ of Chicago
  - UAB = Univ Alabama at Birmingham
- The four numbers will refer to the patient number preceded by the site number
  - 1 = Georgetown
  - 2 = Washington Hospital Center
  - 3 = Hackensack
  - 4 = Univ of Chicago
  - 5 = Univ Alabama at Birmingham
- This will be followed by 2 letters that will be the 2 patient initials (first name, last name)
- Finally, this will be followed by the study name OXEL
  
- Each sample (tissue) will be labeled with the procedure date in MM/DD/YR format and will have a number to indicate the type of collection. Options include:
  - Initial biopsy (tissue) - 1
  - Surgery (tissue) - 2

- Recurrence (tissue) - 3

See Correlative Laboratory Manual for more details regarding sample handling and processing.

## **10.0 ETHICAL CONSIDERATIONS**

### **10.1 Institutional Review Board (IRB)**

GCP requires that the clinical protocol, any protocol amendments, the Investigator's Brochure, the informed consent and all other forms of subject information related to the study (e.g., advertisements used to recruit subjects) and any other necessary documents be reviewed by an IRB. IRB approval of the protocol, informed consent and subject information and/or advertising, as relevant, will be obtained prior to the authorization of drug shipment to a study site. Any amendments to the protocol will require IRB approval prior to implementation of any changes made to the study design. Any serious adverse events that meet the reporting criteria, as dictated by local regulations, will be reported to the IRB. During the conduct of the study, the investigator should promptly provide written reports to the IRB of any changes that affect the conduct of the study and/or increase the risk to subjects.

### **10.2 Ethical Conduct of the Study**

The study will be conducted in accordance with the protocol, ICH guidelines, applicable regulations and guidelines governing clinical study conduct and the ethical principles that have their origin in the Declaration of Helsinki.

### **10.3 Subject Information and Consent**

Prior to the initiation of any screening or study-specific procedures, the investigator or his/her representative will explain the nature of the study to the subject and answer all questions regarding this study. Each informed consent will be reviewed, signed and dated by the subject and the person who administered the informed consent. A copy of each informed consent will be given to the subject and each original will be placed in the subject's medical record. An entry must also be made in the subject's dated source documents to confirm that informed consent was obtained prior to any study-related procedures and that the subject received a signed copy. Tissue sample collection for analysis will only be performed if the subject has voluntarily consented to participate after the nature of the testing has been explained and the subject has had the opportunity to ask questions.

### **10.4 Ethical Consideration for Enrollment**

Only patients with triple negative breast cancer and residual disease at the time of surgery, who have a high risk of recurrence, will be considered for enrollment. As described above, nivolumab alone or in combination with capecitabine is a rational and promising combination for such patients.

